5.2 Equipment

Laboratory evaluations (blood draw)

Blood sampling will be offered at blood draw units and primary care facilities in Göteborg and surrounding municipalities. Analyses of PSA and serum creatinine (only for men undergoing mpMRI) will be performed by Unilabs, Skövde.

Participating blood collection sites:

Nötkärnan Bergsjön vårdcentral och BVC
Nötkärnan Masthugget Familjeläkare och BVC
Nötkärnan Kortedala Vårdcentral och BVC
Nötkärnan Hovås Askim Familjeläkare och BVC
Nötkärnan Friskvåderstorget Vårdcentral och BVC
Nötkärnan Kållerød Familjeläkare och BVC
Carlanderska sjukhuset, Laboratoriet
Carlanderska sjukhuset, Urologkliniken
Noltorp vårdcentral
Vårdcentralen Kusten
Unilabs provtagning Almedal

Imaging (MRI)

A 3 Tesla MRI system with a pelvic surface coil is available for this study at the Dept. of Radiology, Sahlgrenska University Hospital. The imaging protocol is multi-parametric (mpMRI) including T2-weighted, diffusion weighted (DWI) and dynamic contrast-enhanced (DCE) sequences. A "positive MRI" or abnormal / suspicious lesion, will be defined by means

of a centralized evaluation at the radiology department, using the most recent version of the European Society of Urogenital Radiology (ESUR) criteria Prostate Imaging Reporting and Data system (PI-RADS) score. A PI-RADS score of 3-5 will be considered “positive”. A standardized template will be used to report up to three lesions. For each lesion, PI-RADS score, size (largest diameter and its perpendicular diameter), prostate zone (peripheral, transition zone, or both) and location of lesion center (according to the sector system described below) will be recorded. All MRI examinations will be evaluated in consensus by two out of three study radiologists, with 4-10 years of experience in the prostate MR imaging field.

Multiparametric MRI is since April 1st, 2019, and onward only used in screening round 1 (see addendum 7).

All men referred for MRI in subsequent screening rounds (from screening round 2 and forth) undergo bi-parametric MRI (bpMRI) without the dynamic contrast-enhanced MRI sequence.

PI-RADS v2.1 has been used since June 1, 2019 (see Amendment 8).

Histopathological specimens (prostate biopsies)

Biopsy of the prostate will be carried out by a limited number of urologists (n=5), with several years of prostate biopsy experience (5-30 years), using existing equipment at the Dept. of Urology, Sahlgrenska University Hospital. Biopsies are conducted by a B&K equipment and directed by transrectal ultrasound (TRUS) guidance. Fusion biopsies will be used in selected cases but cognitive directed biopsies will be the standard.

On December 14, 2016, the number of cores in systematic biopsies was increased from 10 to 12 cores (see Amendment 9). All 12 cores are directed against the posterior aspect of the prostate. We use the same sector-system as in the National Swedish Prostate Cancer Registry (NPCR) which comprises 12 posterior and 12 anterior sectors. In case of a positive MRI finding in one of the sectors included in the systematic biopsies among men in Arm 1, one of the targeted cores from that sector is appointed as belonging to the “systematic biopsies” and the remaining three cores as targeted. In case of a MRI lesion in a sector not included in the systematic biopsies all 4 cores are designated as targeted.

The MRIs of men with PI-RADS 5 and a negative biopsy will, since January 16, 2020, be demonstrated at a prostate MRI radiology conference and these men will be re-invited after 3 months for a repeated targeted biopsy.

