3 STUDY DESIGN

This is a population-based screening trial with randomization of men into either controls (not invited) or an intervention group invited for screening. Participating men are further randomly allocated into one out of three test arms with different designs following the flow chart in Figure 1. The rationale for randomizing participating men into three groups is based on the main obstacle with current gold standard, i.e. PSA and systematic biopsies which lead to an unacceptably high rate of over-diagnosis of small indolent cancers.

The hypothesis is that switching from systematic biopsies in all men with elevated PSA to targeted biopsies only, and only in men with positive MRI, will strongly decrease the risk of over-diagnosis and thus shift the balance between benefits versus harms so that screening for prostate cancer could be accepted as general health policy. The design is appropriate for testing this hypothesis and will hopefully provide level I evidence as to the preferred screening algorithm incorporating MRI as an adjunct to PSA as compared to the current gold standard, i.e. PSA and systematic biopsies. Performing systematic biopsies blinded to MRI result and thereafter targeted biopsies in arm 1 (see below) makes it possible i) to compare cancers detected by targeted biopsies only with ii) those detected by the combination of systematic and targeted biopsies and iii) those detected by systematic biopsies only. Hence the following comparisons between different diagnostic approaches can be performed after completion of screening round 1:

- Pre-biopsy MRI and MRI-targeted biopsy only vs systematic biopsy and in case of a positive MRI also targeted biopsy (Arm 2-3 vs Arm1 (primary objective); can also be compared within Arm1)
- Pre-biopsy MRI and MRI-targeted biopsy vs systematic biopsy (Arm 2-3 vs Arm1; can also be compared within Arm1)
- Pre-biopsy MRI and systematic biopsy and in case of a positive MRI also targeted biopsy vs systematic biopsy (Within Arm1)
- Pre-biopsy MRI and in case of a positive MRI both targeted biopsy and systematic biopsy vs systematic biopsy (Within Arm1)
- Pre-biopsy MRI and in case of a positive MRI both targeted biopsy and systematic biopsy vs systematic biopsy and in case of a positive MRI also targeted biopsy (Within Arm1)
- Pre-biopsy MRI and in case of a positive MRI both targeted biopsy and systematic biopsy vs pre-biopsy MRI and MRI-targeted biopsy (Within Arm1)

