4 STUDY INTERVENTION

4.1 Intervention

Arm (1) (reference arm)

- Screen-negative: If the total-PSA level is “normal”, i.e. below the cut-off 3.0 ng/mL, no further testing or examination will be performed, but all men will be re-invited.
- Screen-positive: If the total-PSA level is “elevated” above the cut-off i.e. ≥ 3.0 ng/mL, the man will be invited for an MRI.

All men will be recommended standard biopsy, i.e., digital rectal exam followed by TRUS-guided 12-core standard prostate biopsy according to the screening protocol. These standard biopsies will be taken with both the urologist and subject blinded to the MRI result. After these standard biopsies, the study nurse will show the urologist the result from the MRI examination, and in case of suspicious lesion at MRI, 3-4 targeted* biopsies in each of these lesions will be performed in the same séance; 3 targeted biopsies if one of the systematic biopsies already hit the area, and 4 targeted biopsies if otherwise.

- Men in whom MRI for any reason is not achievable or the result is inconclusive will only undergo systematic biopsies

Arm (2) (first experimental arm)

- Screen-negative: If the total-PSA level is “normal”, i.e., below 3.0 ng/mL, no further testing or examination will be performed. The man will be re-invited for screening identical to Arm (1).
- Screen-positive: If the total-PSA level is “elevated” ≥ 3.0 ng/mL, he will be offered MRI.
 - If the MRI is positive (PI-RADS 3-4), only targeted* biopsies will be performed, i.e. 4 biopsy cores targeted against each suspicious lesion, but no systematic biopsies.
 - If the MRI is positive (PI-RADS 5), targeted* biopsies will be performed, i.e., 4 biopsy cores targeted against each suspicious lesion but also systematic biopsies. Changed 2018-10-15 (see amendment 5)
 - If the MRI is negative no biopsies will be performed.
 - If the MRI is negative and PSA ≥ 10 and PSA density (PSAD), ≥ 0.1 , systematic 12-core biopsies will be performed. PSA cut off changed 2016-03-01 from 20 to 10 ng/mL (see amendment 1).
 - Men in whom MRI for any reason is not achievable, or the MRI is technically inferior (for example in men with hip prosthesis), are invited for urological examination with digital rectal examination (DRE) and transrectal ultrasound

(TRUS). These men are included in the intention to screen analysis but not in the per protocol analysis (see 6.2.1).

Arm (3) (experimental arm II)

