MRI pos*	MRI neg	MRI pos **, ***	MRI neg	MRI pos*	MRI neg
12 systematic plus 3-4 targeted biopsies	12 systematic biopsies	4 targeted biopsies. If cancer. 12 additional cores at a later occasion	No biopsies	12 systematic plus 3-4 targeted* biopsies	12 systematic biopsies

- * If the MRI positive sector is sampled with one core in the systematic biopsies, 3 extra targeted biopsies are sampled from that sector, otherwise 4 biopsies
- ** If MRI shows PI-RADS 5, 12 systematic biopsies are added (not in screening round 1)
- ***If cancer is found in the targeted biopsies patients are rescheduled for systematic biopsies

Prostatectomy specimen

Prostatectomy specimen will be processed according to Swedish standard (KVA document) and reviewed at the department of Pathology at Sahlgrenska University Hospital. Tumor volume will be assessed by the planimetric method. Endpoint definitions for prostatectomy specimen are given in table 3, p

Prostate cancer mortality

The project is planned to continue to allow evaluating long-term effects on prostate cancer mortality. In the Göteborg-1 trial [9], an independent Cause of death (COD) committee consisting of 3 urology professors, blinded to study allocation, reviewed the cause of death following a standardized algorithm. A similar COD committee will be used in this study.

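### Section 5.2 counts an MRI-aimed core in arm 1 as systematic, against sections 3, 4.1 and 5.1; followed literally, this biases the biopsy-method comparisons but not the primary analysis

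*Protocol*

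**What the plan says.** Four parts of the protocol bear on which arm 1 core carries which label.

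- **Section 3** gives the reason for the arm 1 design: "Performing systematic biopsies blinded to MRI result and thereafter targeted biopsies in arm 1 (see below) makes it possible" to separate cancers found by targeted cores only, by both methods together, and by systematic cores only. It then lists six comparisons for the end of screening round 1.
- **Section 4.1, arm 1**: "These standard biopsies will be taken with both the urologist and subject blinded to the MRI result". The MRI result is shown afterwards, and the number of added cores is "3 targeted biopsies if one of the systematic biopsies already hit the area, and 4 targeted biopsies if otherwise". In arms 2 and 3, an MRI lesion gets four targeted cores.
- **Section 5.1, footnote to the biopsy table**: "If the MRI positive sector is sampled with one core in the systematic biopsies, 3 extra targeted biopsies are sampled from that sector", and four otherwise. The table gives MRI-positive men in arm 1 twelve systematic cores and three or four targeted ones.
- **Section 5.2, histopathological specimens**: "All 12 cores are directed against the posterior aspect of the prostate", within a scheme that has twelve posterior sectors and as many anterior ones. When an arm 1 lesion lies in a sampled sector, the stated rule is that "one of the targeted cores from that sector is appointed as belonging to the" set of systematic cores, while the other three count as targeted. For lesions elsewhere: "In case of a MRI lesion in a sector not included in the systematic biopsies all 4 cores are designated as targeted".

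**The concern.** In 4.1 and 5.1, the lesion-area core credited to systematic biopsy is one taken before anyone at the biopsy knew the MRI result. In 5.2, as worded, it is one of the cores aimed at the lesion. The two rules differ in exactly the property on which section 3 relies. Section 5.2 is also the sentence that explicitly assigns labels, so an analyst building the systematic-only and targeted-only results would naturally follow it.

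The triggers differ as well. Section 4.1 asks whether a systematic core hit the area. Section 5.1 asks whether the sector was sampled. Section 5.2 asks only whether the sector belongs to the systematic scheme. Because all 12 systematic cores are posterior and there are 12 posterior sectors, the 5.2 rule could apply to most posterior lesions.

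At stake are the results that separate the two methods. A systematic set containing an aimed core no longer shows what MRI-blind sampling would have found.

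**Working it through.** **1. Core counts for one lesion in a sampled sector**

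| Rule | Blinded cores taken | Aimed cores taken | Labelled systematic | Labelled targeted |
|---|---|---|---|---|
| 4.1 and 5.1 | 12 | 3 | 12 (all blinded) | 3 |
| 5.2 literally, aimed core added | 12 | 4 | 12 + 1 = 13 | 3 |
| 5.2 literally, aimed core replaces a blinded one in the set | 12 | 4 | 11 + 1 = 12 | 3 |

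The second row does not fit the 12 systematic cores in the 5.1 table. The third fits the count only by dropping a blinded core from the systematic set. For lesions outside the sampled sectors, every version leaves four targeted cores and there is no conflict.

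**2. Which section 3 comparisons are exposed**

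- Comparisons 2, 3 and 4 have systematic biopsy alone on one side. Its yield is overstated within arm 1 and, in comparison 2, also in arms 2-3 versus arm 1.
- Comparison 1 (its within-arm-1 version) and comparison 6 set targeted-only against the combined set. The targeted side is credited with three of the four aimed cores.
- Comparison 5 uses all cores on both sides in MRI-positive men, so labels cannot change it.
- The primary and secondary contrasts (sections 2.5, 6.2.1 and 6.2.2) use arm 1 systematic and targeted cores together. Moving a core from one label to the other does not alter the pooled result.

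**3. Illustration of size**

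The protocol gives no per-core detection figures, so these inputs are assumptions: independent cores, hit probability q per aimed core, and blinded systematic detection s = 0.70 of MRI-visible lesions.

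- Targeted, three cores: T3 = 1 − (1 − q)³
- Systematic under 4.1 and 5.1: s = 0.70
- Systematic under literal 5.2 (aimed core added): s + (1 − s)q = 0.70 + 0.30q

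| q | T3 | Systematic, literal 5.2 | Gap, 4.1 and 5.1 | Gap, literal 5.2 | Shift = 0.30q |
|---|---|---|---|---|---|
| 0.3 | 65.7% | 79% | −4.3 | −13.3 | 9 points |
| 0.5 | 87.5% | 85% | 17.5 | 2.5 | 15 points |
| 0.6 | 93.6% | 88% | 23.6 | 5.6 | 18 points |

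**4. Replacement variant**

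Here only the lesion sector is considered, with assumed hit probability 0.4 for the blinded core and 0.65 for an aimed core. T3 = 1 − 0.35³ = 0.957.

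- 4.1 and 5.1: 0.957 − 0.40 = 0.557
- 5.2 with replacement: 0.957 − 0.65 = 0.307
- 5.2 with addition: 0.957 − (1 − 0.60 × 0.35) = 0.957 − 0.79 = 0.167

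The replacement result needs an aimed core to hit more often than a blinded one. With blinded 0.6 and aimed 0.5 the gap moves the other way, from 0.875 − 0.60 = 0.275 to 0.875 − 0.50 = 0.375. In the addition variant the systematic yield can only rise or stay level, whatever the dependence between cores.

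**5. Three versus four aimed cores**

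Four aimed cores at q = 0.5 detect 1 − 0.5⁴ = 93.75%, against 87.5% with three, a difference of 6.25 points. For sampled sectors this difference between arm 1 and arms 2-3 exists under 4.1 and 5.1 too, without any relabelling.

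**The case against.** The best defence is that 5.2 is loose wording for the rule in 4.1 and 5.1. Its arithmetic matches: four cores in the lesion sector, one counted as systematic and three as targeted, or all four targeted if the sector is not sampled. The core it appoints could be the systematic core already taken there. The section sits under equipment, while the intervention section and the biopsy reference table both keep the blinded core. This reading is plausible, and it is why the point is a contradiction to resolve and not proof that cores were mislabelled. It does not remove the need for correction, because the sentence as written says the opposite.

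The exposed comparisons are also ones that section 3 says can be performed, and section 6.2 plans no test for them. That limits the weight of the point. They remain a stated purpose of the arm 1 design.

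The illustration rests on independent cores. Section 5.2 makes cognitive targeting the standard, and an aiming error could affect all cores aimed at one lesion together. The sizes are therefore illustrative only.

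A reader might infer more than the text supports:

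- *That blinding is broken.* It is not. The urologist takes the standard cores before seeing the MRI, and later labelling cannot undo that. What is lost is the MRI-blind origin of the set called systematic.
- *That the whole error disfavours MRI-targeted biopsy.* This holds for detection yield, such as significant cancer. For insignificant cancer, extra detections count against systematic biopsy. An aimed core may also turn a Gleason 6 result into a higher grade, so the number can move either way.
- *That the gap shrinks from 23.75 to 2.5 points.* That starts from four aimed cores (93.75% v 70%). Of the 21.25 points lost, 6.25 come from the three-versus-four-core difference and only 15 from the relabelling.

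**Conclusion.** The concern stands as an internal contradiction with a definite consequence if 5.2 is followed as written. In that case the arm 1 systematic set contains an MRI-aimed core, and the yield of systematic biopsy alone is overstated. With an aimed core added and the stated assumptions, the shift is 9 to 18 points for q from 0.3 to 0.6; at q = 0.5 the gap goes from 17.5 to 2.5 points. In the replacement variant, the direction depends on aimed cores hitting more often than blinded ones.

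The effect is confined to lesions in systematically sampled sectors and to results that split arm 1 by biopsy method. It does not reach the primary or secondary contrast or the fifth comparison in section 3. The documents do not show which rule was applied in practice.

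**What to change.** Reconcile section 5.2 with sections 4.1 and 5.1, including the trigger (area hit, sector sampled, or sector in the scheme), so that one rule states which arm 1 core carries which label.

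For analysis of arm 1, define systematic cores as those taken before the MRI result was disclosed and targeted cores as those taken after. Apply this to every comparison in section 3 that separates the two methods.

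As a sensitivity analysis only, also count the blinded core in the lesion sector towards the targeted strategy, because for such lesions arm 1 has three aimed cores where arms 2 and 3 have four. This should not be the main analysis, since it credits the targeted strategy with a core that was not aimed.

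No change to biopsy practice is asked for. The cost is wording and relabelling. Section 5.1 says that cancer-bearing cores are reviewed separately, but the protocol does not state that each core's blinded or directed origin was recorded. If it was not, the investigators should say which labelling rule was used and report the split results with that limitation.

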6 STATISTICAL CONSIDERATIONS

6.1 Sample Size Calculation

The hypothesis is that the MRI-targeted biopsy only strategy would reduce insignificant cancer with 50%. Based on previous studies and expert knowledge, we assumed that the proportion of men diagnosed with insignificant cancer among men with PSA ≥ 3 in Arm 1 (reference arm) would be 9%. This gave a sample size of N=1,164 men with PSA ≥ 3 ng/mL to achieve 80% power, when having a two-sided test alternative and significance level 5%. Furthermore, we hypothesized that 7% among men attending PSA-screening would have an elevated PSA and that the participation rate would be 50%, which lead to the sample size N=33,260 altogether in the three screening-arms. Accounting for uncertainty in the hypothesized proportion of insignificant cancers and in the proportion of men with PSA ≥ 3

ng/mL among those screened, lead to the final sample size of N=36,000 for the SG. With an allocation rate of 1:2 between the CG and SG, altogether, N=54,000 men are needed to be included in the study.

6.2 Analysis plan for the primary and secondary endpoints

6.2.1 Primary objective (Detection of insignificant cancer)

- Hypothesis

The proportion of men with insignificant cancer detected by PSA testing with threshold 3 ng/mL, systematic biopsies and MRI-targeted biopsies (p_1) will be different from the proportion detected when omitting systematic biopsies (p_2):

H_0 (null hypothesis): $p_1 = p_2$

H_A (alternative hypothesis): $p_1 \neq p_2$

Although the hypothesis of the investigators is one-sided, that MRI-targeted biopsies only will lower the proportion, the test is two-sided to allow for a significant effect in both directions.

- Analysis populations

First assessment (after completion of screening round 1): All men in arm 1 will be compared to all men in arm 2 and 3 combined. However, for men in arm 3, cancers detected in men with PSA < 3 ng/mL will be ignored.

Later assessments: the analysis will compare all men in arm 1 with all men in arm 2.

The analyses will primarily be carried out according to the intention to treat (ITT) principle, which here means that all men will be included in the analysis and belong to the arm they were allocated to, irrespective of whether they completed the intended diagnostic pathway with MRI and biopsies or not.

Furthermore, per protocol analyses will be carried out including only men who strictly follow the protocol.

An additional analyses will compare men in arm 1 who underwent MRI followed by systematic and possible targeted biopsies (if MRI positive) with those in arm 2 and 3 who underwent MRI and also targeted biopsies but ignoring results from possible systematic biopsies if those were taken at the primary biopsy and the targeted biopsies were benign.

- Analysis

Outcome measure is the relative difference of the proportion of insignificant cancers detected in arms 2 and 3 combined vs arm 1 (the cancers detected in men with PSA below 3 ng/mL in arm 3 will be ignored). In later assessments only arm 1 and 2 will be included. The result will be presented as a point estimate with a two-sided 95% confidence interval, and a p-value of the hypothesis test. Significance testing will only be carried out for the first definition of insignificant cancer (Gleason grade 3+3). The score method will be used for testing and confidence intervals (27). A p-value below 5% will be considered statistically significant.

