2.1 Primary objectives

The primary objective of the trial is to evaluate whether changing the screening algorithm in men with PSA ≥ 3 ng/mL from systematic biopsy to MRI-targeted biopsy only, can reduce the risk of detecting clinically insignificant cancers.

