3.5 Allocation of Screening Group to three study arms

Men randomized to the screening group and who accept participation will be randomly allocated 1:1:1 into one of the three study arms. Allocation to study arm will occur automatically and instantly the first time a man has a PSA test delivered to the central database. PSA test results are delivered electronically directly into the database from the central laboratory and there is no manual interference.

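### The round 1 primary test compares crude proportions in all allocated men; stratifying by the PSA known before allocation (<3 vs ≥3 ng/mL) would give a slightly more precise estimate from data already held

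*Protocol*

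**What the plan says.** - **Objective (Protocol 2.1).** The trial asks "whether changing the screening algorithm in men with PSA ≥ 3 ng/mL from systematic biopsy to MRI-targeted biopsy only" lowers the risk of finding insignificant cancer.
- **Sample size (Protocol 6.1).** The assumption is that "the proportion of men diagnosed with insignificant cancer among men with PSA ≥ 3 in Arm 1 (reference arm) would be 9" percent, and that the "MRI-targeted biopsy only strategy would reduce insignificant cancer with 50" percent. This leads to "N=1,164 men with PSA ≥ 3 ng/mL to achieve 80% power, when having a two-sided test alternative and significance level 5" percent. With 7% of attendees having elevated PSA and 50% participation, 6.1 arrives at 33,260 invited, then raises this to 36,000.
- **Primary analysis (Protocol 6.2.1).** The population is as-allocated: "all men will be included in the analysis and belong to the arm they were allocated to". At the first assessment arm 1 is compared with arms 2 and 3 combined, and arm 3 cancers found below PSA 3 are not counted. The measure is a relative difference of proportions, tested by the score method. No stratum or covariate is named.
- **Secondary analysis (Protocol 6.2.2).** Significant cancer is handled the same way, without a test.
- **Timing of PSA (Protocol 3.5).** "Allocation to study arm will occur automatically and instantly the first time a man has a PSA test delivered to the central database".

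**The concern.** The planning figures count men with PSA ≥ 3, while the test uses everyone with a PSA result. In round 1, arms 1 and 2 have no work-up below 3 ng/mL (Protocol 4.1), and arm 3 findings below 3 are set aside. The lower PSA group therefore adds to the denominator and essentially nothing to the numerator.

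If one arm happens to receive a larger share of men with PSA ≥ 3, the crude proportion in that arm rises for a reason unrelated to the biopsy strategy, and the crude test treats the difference as noise. PSA at allocation is the strongest predictor of the outcome, is recorded for every allocated man and cannot be influenced by the arm. What is at stake is some precision in the primary result, and in the interval for significant cancer, where 6.2.2 offers no test and the interval carries the message.

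**Working it through.** **1. The plan's own figure.** Inputs from 6.1: 9% vs 4.5%, two-sided 5%, 80% power. Allocation 1:1:1 (3.5) makes the comparison 1:2.
- Pooled-variance formula: p̄ = (0.09 + 2×0.045)/3 = 0.06; n₁ = [1.96√(0.06×0.94×1.5) + 0.8416√(0.09×0.91 + 0.045×0.955/2)]² / 0.045² ≈ 349, taken as 350; total 1,050.
- With continuity correction: 382 + 764 = 1,146, which is 1.5% below 1,164. The unpooled formula gives about 1,202. The plan does not name its formula, but 1,164 is consistent with these.
- 1,164/0.07 = 16,629 attendees; /0.5 = 33,257, matching 33,260.

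**2. Numbers per side.** PSA ≥ 3: 388 vs 776. All attendees: 5,543 vs 11,086. Expected events are 0.09×388 = 34.92 and 0.045×776 = 34.92 on either denominator. The all-men proportions are 0.63% and 0.315%. The relative risk is 0.50 both ways.

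**3. Why stratifying equals conditioning on PSA ≥ 3 in round 1.** With Mantel–Haenszel weights, a stratum without events adds zero to both numerator and denominator of the relative risk, and zero to the test statistic and its variance. The figures for PSA ≥ 3 are therefore the stratified figures, provided that stratum <3 has no counted events.

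**4. Variance of the log relative risk** = (1/x₁ − 1/n₁) + (1/x₂ − 1/n₂):
- All men: 2/34.92 − 1/5,543 − 1/11,086 = 0.0570 (SE 0.239).
- Stratified: 2/34.92 − 1/388 − 1/776 = 0.0534 (SE 0.231).
- Ratio 0.937, a 6.3% reduction. The difference, 0.0036, equals 0.93/388 + 0.93/776, which is the variance of the log ratio of the PSA ≥ 3 shares. So the gain is exactly the removed imbalance.
- 95% interval around 0.50: 0.313–0.798 crude, 0.318–0.786 stratified.

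**5. Power** = Φ{[|p₁−p₂| − 1.96√(p̄(1−p̄)(1/n₁+1/n₂))] / √(p₁(1−p₁)/n₁ + p₂(1−p₂)/n₂)}:
- Stratified: (0.0450 − 0.0289)/0.0163 = 0.984, giving 83.7%.
- All men: (0.003150 − 0.002085)/0.001189 = 0.896, giving 81.5%.
- Simulation (400,000 runs): 0.8242 crude and 0.8445 stratified. At 36,000 invited: 0.850 and 0.870 (formula 84.2% and 86.3%).
- Simulated type I error, 6% in both arms: 4.99% crude, 4.96% stratified. Under the planning alternative the simulated mean log relative risk is −0.694 for both.

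**6. Sensitivity.** With 36,000 invited, and assuming a PSA ≥ 3 share of 5–10% and an arm 1 rate of 6–17%, the variance falls by 4–12% and power rises by 0.2–3.0 points.

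**7. Significant cancer.** The protocol gives no rate. Assuming r = 10%, 15% or 20% of men with PSA ≥ 3 in both arms, the variance ratio is (1−r)/(1−0.07r) = 0.906, 0.859 or 0.811, a fall of 9%, 14% or 19%.

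**The case against.** The best case for leaving the plan alone has four parts.

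- **The crude analysis is legitimate.** Detection per screened man is a sensible measure for a population screening trial, and the wording of 2.1 can be read as saying where the algorithm changes rather than fixing a denominator. This stands. A reader might infer from the different denominators that the trial is underpowered or that the powered analysis is undermined. The documents do not support that: 6.1 carries the 1,164 through to invited men and adds a margin, the target relative risk is the same, and the crude test exceeds 80%.
- **Stratification belongs in the analysis plan.** This stands only in part. 6.2.1 itself fixes population, measure, test and interval method, so a later plan that stratified would alter the stated primary analysis.
- **The gain is small.** True, and it sets the severity.
- **Finer strata or later rounds could undo it.** This stands as a limit. A reader might want a separate stratum at PSA ≥ 10, but arms 2 and 3 also receive systematic biopsies at PSA ≥ 10 with PSA density ≥ 0.1 (4.1, 4.4 and the table in 5.1). The biopsy contrast largely disappears there, and a common relative risk is doubtful. A reader might also carry the gain to later assessments or restrict them to entry PSA ≥ 3. Men below 3 at entry can become cases later, so neither follows.

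**Conclusion.** The point holds as a minor improvement in precision and consistency. The crude intention-to-treat test in 6.2.1 is valid and adequately powered for its stated target. It leaves out a true pre-allocation covariate and so keeps chance imbalance in the PSA ≥ 3 share within its error. Stratifying would cut the variance of the log relative risk by about 6% and raise power by about 2 points, without changing the target relative risk or the type I error.

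This rests on the planning values in 6.1, essentially no counted round 1 events below PSA 3, and a common relative risk among men with PSA ≥ 3. It is confined to the first assessment.

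**What to change.** In Protocol 6.2.1, for the first assessment:

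1. Keep every man in his allocated arm, and specify the score method stratified by the PSA that triggered allocation (<3 vs ≥3 ng/mL), with the weights stated (Mantel–Haenszel weights match the figures above).
2. Report the crude result per screened man beside it.
3. Apply the same stratification to the interval for significant cancer in 6.2.2.
4. State in 6.1 and 6.2.1 that 9% and N=1,164 refer to men with PSA ≥ 3.
5. Add no separate stratum at PSA ≥ 10. At later assessments entry PSA may be a stratum but not a restriction, and no gain should be claimed from the round 1 calculation.

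The cost is a few sentences; PSA is already in the database for every allocated man. One caution: 9.3.1 says that round 1 was completed in 2021. If outcomes by arm had already been seen when the change is made, the stratified result should be labelled supplementary and the crude test kept as primary.
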